#### 8.9 First Dose Plan

The dosing schedule for all cohorts is intended to minimize potential risk to subjects' safety. It is known that the types, severities, time courses and pharmacokinetic correlates of adverse effects observed in preclinical studies are not necessarily predictive of experience in human subjects, at any dose. This plan further recognizes that major acute toxicities of pharmaceuticals in human subjects may on rare occasions not be predicted by preclinical

experience, warranting additional caution in administering first doses to humans. As such caution has been advised in particular regarding biopharmaceuticals, it is noted that Nu-3 is not categorized as a biopharmaceutical. A traditional risk-reduction strategy has been to apply large safety factors (divisors of human equivalent doses corresponding to NOAELs in appropriate animal toxicology models) in determining the Maximum Safe Starting Dose for first-in-human study. A further risk-reduction strategy, adopted here, is to separate first and second exposures more widely in time than has been typical study procedures.

Preclinical experience suggests that possible adverse effects after a single dose topical exposure to NU-3 would be unlikely. Accordingly, the dose plan is as follows:

- Qualified patients for all Cohorts are screened from Day -7 to -4 hours. Patients understand (disclosed in informed consent) that their qualification for enrollment is not finalized until the time of enrollment. They understand that their order of enrollment is randomly determined.
- On Day -7 to -4 hours, baseline procedures are performed (demographics and medical history, and limited physical examination per protocol, urine pregnancy test (if applicable), baseline laboratory tests (blood chemistries, hematology, coagulation profile, and urinalysis), and baseline subject disease assessments).
- On Day 1, the patients is randomized and dosed to either Nu-3 or Placebo.
- On the next following day, Day 2, if the Investigator observes no dose-limiting toxicity (Section 8.10.6) in the patient dosed on Day 1, the Investigator will distribute the investigational product kit and instructed to apply the product twice daily for one (1) week (7 days).
- If the Investigator observes a suggestion of dose-limiting toxicity, the procedure specified in Section 8.10.3 is followed.

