#### 8.10.5 **Decision Criteria**

8.10.5.1 Stopping of Dose Administration and/or Escalation

Further study drug dose administration or escalation will be stopped:

- 1. by Sponsor, for any reason at any time;
- 2. by Principal Investigator or Safety Review Committee, if subjects' safety is considered to be at unacceptable risk;
- 3. by Safety Review Committee, according to these criteria:
  - If 2 or more of the Nu-3-treated subjects in a cohort experience a DLT, dose escalation is stopped;
  - If 1 of the Nu-3-treated subjects experiences a DLT, the cohort is expanded to include 4 additional subjects (Nu-3:Placebo ratio of 3:1); and
  - If 2 or more of the Nu-3-treated subjects in the expanded cohort (of 8+4=12 subjects) experience a DLT, dose escalation is stopped;
  - If only 1 of the Nu-3-treated subjects in the expanded cohort experiences a DLT (i.e., no additional subjects experience a DLT following cohort expansion), stopping of dose escalation is not required.

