### 8.10.5.2 Definition of Dose-Limiting Toxicity (DLT)

Dose-Limiting Toxicity in an individual subject is defined as any Grade 2 or higher Adverse Event (AE) toxicity according to National Cancer Institute Common Terminology Criteria for Adverse Events, Version 3.0 (CTCAE – See Appendix 16.1) that is considered by the Investigator to be at least possibly related to study drug.

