the study, whether blinded or unblinded. AEs may be either spontaneously reported or elicited during questioning and examination of a subject. All AEs must be completely recorded on the within the electronic source document system. If known, the Investigator should report the diagnosis of the underlying illness or disorder, rather than its individual symptoms. Subjects experiencing AEs that cause interruption or discontinuation of test article, or those experiencing AEs that are present at the end of their participation in the study will receive follow-up as appropriate. If possible, report the outcome of any AE that caused permanent discontinuation or that was present at the end of the study particularly if the AE was considered by the investigator to be definitely, probably, or possibly related to test article.

The investigator will instruct the subject to report any adverse events that may occur during the study. At each visit, the investigator will ask the subject, in non-directive fashion, about any change in the subject's overall condition since the previous visit.

The severity of each adverse event, as judged by the Investigator, will be graded according to Common Terminology Criteria for Adverse Events v4.02 (CTCAE). For AEs not listed in the CTCAE table, the severity of adverse changes in physical signs or symptoms will be classified as follows (consistent with CTCAE):

**Grade 1 Mild** - asymptomatic or mild symptoms; clinical or diagnostic observations only; intervention not indicated.

**Grade 2 Moderate** - minimal, local or noninvasive intervention indicated; limiting age-appropriate instrumental activities of daily living.

**Grade 3 Severe** - medically significant but not immediately life-threatening; hospitalization or prolongation of hospitalization indicated; disabling; limiting self-care activities of daily living.

Grade 4 Life-threatening - urgent intervention indicated.

Grade 5 Death - Death related to AE.

The investigator must determine the relationship of the AE to the test article according to the following categories:

**Definite** - An event that follows a reasonable temporal sequence from administration of the test article; that follows a known or expected response pattern to the test article; and that is confirmed by improvement on stopping or reducing the dosage, and reappearance of the event on repeated exposure (re-challenge).

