**Probable** - An event that follows a reasonable temporal sequence from administration of the test article; that follows a known or expected response pattern to the test article; and that is confirmed by improvement on stopping or reducing the dosage of the test article; and that is unlikely to have been caused by concurrent/underlying illness or other drugs, procedures, or other causes.

**Possible** - An event that follows a reasonable temporal sequence from administration of the test article; that follows a known or expected response pattern to the test article; but may have been caused by concurrent/underlying illness, other drug, procedure, or other causes.

**Unlikely** - An event that does not follow a reasonable temporal sequence from administration of the test article; that does not follow a known or expected response pattern to the test article, or most likely was caused by concurrent/underlying illness, other drug, procedure, or other causes, because of their known effects.

**Not Related** - An event almost certainly caused by concurrent/underlying illness, other drug, procedure, or other causes.

An **adverse reaction** is any AE caused by a drug. Adverse reactions are a subset of all suspected adverse reactions for which there is reason to conclude that the drug caused the event. For the purposes of prescription drug labelling, the term adverse reaction means an undesirable effect, reasonably associated with the use of a drug that may occur as part of its pharmacological action or may be unpredictable in its occurrence.

A **suspected adverse reaction** is any adverse event for which there is a reasonable possibility that the drug caused the event.

For the purposes of safety reporting, "reasonable possibility" means there is evidence to suggest a causal relationship between the drug and the adverse event. A suspected adverse reaction implies a lesser degree of certainty about causality than adverse reaction, which means any adverse event caused by a drug.

An event that is a **serious adverse event (SAE)** must be recorded on the AE eCRF and requires expeditious handling to comply with regulatory requirements.

An adverse event or suspected adverse reaction is considered "serious" if, in the opinion of either the investigator or sponsor, it results in any of the following outcomes:

- Death.
- Life-threatening event.
- Inpatient hospitalization or prolongation of existing hospitalization.

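### Section 13.4 requires a known or expected response pattern for every related category, so a well-timed Grade 2+ event of a new kind may be left out of the DLT count

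*Protocol*

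**What the plan says.** Section 13.4 makes the scale mandatory: "The investigator must determine the relationship of the AE to the test article according to the following categories". Definite, Probable and Possible each require a reasonable temporal sequence together with a known or expected response pattern. For Possible the second condition reads "that follows a known or expected response pattern to the test article; but may have been caused by concurrent/underlying illness" or another cause. Absence of a pattern appears only under Unlikely, which covers an event "that does not follow a known or expected response pattern to the test article, or most likely was caused by concurrent/underlying illness" or another cause.

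Section 8.10.5.2 defines a DLT as a Grade 2 or higher event "that is considered by the Investigator to be at least possibly related to study drug". It does not say which scale applies. Section 8.10.5.1 acts on the count: "If 1 of the Nu-3-treated subjects experiences a DLT, the cohort is expanded to include 4 additional subjects", and 2 or more DLTs stop escalation. Section 8.9 releases the 7-day kit on Day 2 "if the Investigator observes no dose-limiting toxicity (Section 8.10.6) in the patient dosed on Day 1"; the DLT definition is in fact in 8.10.5.2.

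Two other parts of Section 13.4 set no pattern condition. A suspected adverse reaction is defined by a reasonable possibility of causation, and an adverse reaction is said to be possibly unpredictable. The section also provides for reporting suspected reactions that are serious and unexpected.

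**The concern.** The protocol describes the study as first-in-human (Section 8.8), and Section 8.9 warns that "major acute toxicities of pharmaceuticals in human subjects may on rare occasions not be predicted by preclinical" experience. An event unlike anything seen before is therefore one the DLT count most needs to capture. Yet under the literal scale such an event, however well timed, meets none of the three related definitions. If the conditions in Unlikely are alternatives, it is Unlikely. If they are cumulative, it falls into a gap unless another cause is most likely. No text makes timing alone enough for Possible.

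Section 13.4 is the only causality scale in the current five-cohort protocol. It describes related events in the same vocabulary ("particularly if the AE was considered by the investigator to be definitely, probably, or possibly related to test article"), and SAP Section 9.1 tabulates by its five categories, so an investigator deciding on a DLT would naturally use it. At stake is a rule that turns on a single event: 0, 1 or 2 counted DLTs among 8 Nu-3 subjects mean escalate, expand or stop.

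**Working it through.** The plan states no operating characteristics for the DLT rule and no sample size calculation, so there is no figure to reproduce.

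**Step 1: the wording.** Take a Grade 2 event with reasonable timing and no known or expected pattern.

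- Definite, Probable and Possible: the pattern condition fails in each.
- Unlikely: met if its clauses are alternatives; not met if they are cumulative and no other cause is most likely.
- Suspected adverse reaction (same section): can be met, because only a reasonable possibility is needed. The DLT definition does not use this term.

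**Step 2: effect of one uncounted DLT on the rule.** Inputs from the protocol: 8 Nu-3 subjects per cohort (Section 8.4); 1 DLT expands by 4 subjects at 3:1, and 2 stop escalation (Section 8.10.5.1). The 3:1 ratio gives m = 3 added Nu-3 subjects; the same section also writes the expanded cohort as 8+4=12, so m = 4 is shown too. Assumptions: one true DLT among the first 8 is not counted, the other 7 and the added subjects have counted DLT rate p, and subjects are independent.

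- If the other 7 have 0 counted DLTs, probability (1−p)^7, expansion becomes no expansion.
- If they have 1, probability 7p(1−p)^6, stop becomes expand.
- P(next step changes) = (1−p)^7 + 7p(1−p)^6.
- P(final stop/no-stop result changes) = (1−p)^7[1−(1−p)^m] + 7p(1−p)^6(1−p)^m.

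| p | (1−p)^7 | 7p(1−p)^6 | Next step changes | Final result changes, m=3 | m=4 |
|---|---|---|---|---|---|
| 5% | 69.8% | 25.7% | 95.6% | 32.0% | 33.9% |
| 10% | 47.8% | 37.2% | 85.0% | 40.1% | 40.9% |
| 20% | 21.0% | 36.7% | 57.7% | 29.0% | 27.4% |
| 30% | 8.2% | 24.7% | 32.9% | 13.9% | 12.2% |

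**Step 3: price of a wider definition.** With counted rate q per Nu-3 subject, P(stop) = 1 − (1−q)^8 − 8q(1−q)^(7+m). For m = 3:

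- q = 5%: 1 − 0.6634 − 0.2395 = 9.7%.
- q = 6%: 1 − 0.6096 − 0.2585 = 13.2%.
- q = 7%: 1 − 0.5596 − 0.2710 = 16.9%.

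For m = 4 these are 10.9%, 14.7% and 18.8%. Across the protocol's five cohorts, with constant and independent rates, the chance that the rule calls a stop at least once is 1 − (1−P)^5: about 40%, 51% and 60% (m = 3).

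**The case against.** There is a good case that little turns on this.

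- **The DLT link is inferred.** Section 8.10.5.2 asks for the investigator's judgement and does not cite Section 13.4, so an investigator may call a new event possibly related in the ordinary sense. A reader might infer that the protocol requires such events to be excluded; it does not.
- **Few events are exposed.** Known or expected is not a closed list. The reactions in Section 12.7 are open-ended and extend to systemic reactions of any kind, so common ulcer events can already be rated Possible.
- **Section 13.4 itself accepts unpredictable and unexpected reactions**, which weighs against the strictest reading.
- **Other controls do not need a causality rating.** The investigator or committee may stop at discretion (8.10.5.1). The committee must be unanimous and may repeat or lower a dose (8.10.2). In Cohort 1, an adverse event around the wound after Day 1 dosing suspends dosing (8.10.3). An adverse event that may significantly affect the subject requires withdrawal (9.2). On Day 2, a mere suggestion of a DLT invokes the 8.10.3 procedure (8.9), and the investigator separately examines the ulcer before giving out the kit (12.4). So the Day 2 release does not rest on the DLT call alone.

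All of this stands, and it narrows the point. It does not remove it. The controls can prevent harm, but they neither correct the DLT count nor trigger the 4-subject expansion. The reasonable-possibility text leaves the five categories unamended, so the section gives the investigator two different standards. SAP Section 9.1 treats a missing relationship as definite, but only in one summary table, so it does not repair the count during escalation.

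**Conclusion.** The point holds as a defect of wording in a rule that feeds dose decisions. Section 13.4 read literally gives a well-timed event of a new kind no related category, and such an event may be left out of the DLT count. The text does not say it must be.

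The frequency cannot be estimated from the documents. Given one miss, the numeric rule's next step changes with probability 96%, 85%, 58% or 33%, and its final result with about 32%, 40%, 29% or 14%, at assumed counted rates of 5%, 10%, 20% or 30% and with 3 added Nu-3 subjects. A reader might take 96% as the chance of a wrong escalation decision. That is not supported: it is conditional on a miss having occurred, and it includes cases where stop becomes expand and the expanded cohort then stops anyway. Both sets of figures describe the DLT rule alone; discretionary stopping may override it. Nor do the documents support the inference that new toxicity would go unaddressed, given the controls listed above.

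**What to change.** Make three edits.

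1. In Section 13.4, define Possible as an event that follows a reasonable temporal sequence and for which a causal link to the test article cannot reasonably be excluded, whether or not another cause is plausible and whether or not it matches a known pattern. Treat a known pattern as supporting evidence only. Striking the pattern clause alone would not do: the remaining text still presupposes a possible alternative cause, so a well-timed new event with no other explanation would still have no related category.
2. In Unlikely, state that lack of a known pattern does not suffice on its own.
3. In Section 8.10.5.2, state that DLT attribution uses this scale at Possible or above, consistent with the reasonable-possibility standard.

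No new data are needed. The cost is that some background events may be counted. If the change adds 1 or 2 percentage points to an assumed counted rate of 5%, rule-based stopping rises from 9.7% to 13.2% or 16.9% per cohort, and from about 40% to 51% or 60% across five cohorts under the Step 3 assumptions. A tolerable dose may thus be stopped more often. For a first-in-human study with safety as its primary objective, that is a reasonable trade, but the sponsor should make it knowingly.

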#### 14 ASSESSMENT OF EFFICACY

### 14.1 Primary Efficacy Endpoint Assessment

The primary efficacy endpoint is to assess the microbiological response to bisphosphocin™ Nu-3 as determined by reduction of pathogenic bacteria following Nu-3 treatment. The microbiological assessments from the local lab will be used to measure aerobic and anaerobic culture and sensitivity at screening, after a single dose treatment (Day 1), after a second dose treatment (Day 2), after twice daily for 7 day treatment, at Day 15.

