### 12.3 Visit 2 (Day 1) SAD Treatment

Patients will return after the screening visit for Single Ascending Dose Treatment. Patient disease assessments will be performed as specified in the schedule of events table.

- Vital signs (blood pressure, heart rate, temperature) will be examined within 10 minutes prior to the start of treatment
- Baseline Patient Disease Assessment: Visual examination of chronic ulcer, score target ulcer using DUSS Scoring System, Swab wound to culture for microbiological examination Not applicable if Visit 2 is the same day as Screening Visit
- Photo Documentation and Calculation of the Ulcer Area and Depth using the Aranz Medical SilhouetteTM system - Not applicable if Visit 2 is the same day as Screening Visit

In SAD Treatment, eligible patients will be treated with a single application of Test Product. Test Product will be administered to the infected diabetic foot ulcer and surrounding intact skin at a dose of 1 to 3 drops from a dropper bottle per 1 cm^2 of ulcer area, left open to air for 5 minutes and then dressed using Owens gauge, Kerlex and tape. The ulcer with a non-abrasive bandage following the initial observation period and the patient will be released with verbal instructions to leave the bandage on the wound and return for a follow up visit within  $24 \text{ h} \pm 2 \text{ h}$ .

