### 12.4 Visit 3 (Day 2 [24 h $\pm$ 2 h.]) MAD Treatment

Patients will return after the Single Ascending Dose Treatment. Patient disease assessments will be performed as specified in the schedule of events table.

- Vital signs (blood pressure, heart rate, temperature) will be examined within 10 minutes prior to the start of treatment
- Baseline Patient Disease Assessment: Visual examination of chronic ulcer, score target ulcer using DUSS Scoring System, Swab wound to culture for microbiological examination
- Photo Documentation and Calculation of the Ulcer Area and Depth using the Aranz Medical SilhouetteTM System

The Principal Investigator will visually exam the chronic ulcer to determine if a patient is eligible to continue in the study. Eligible patients will be provided with his/her designated test product kit and instructed to apply the product twice daily for one (1) week (7 days). Test product application will be demonstrated, and patient instruction sheet reviewed, using the assigned test product. The patients will be observed applying the first dose in the clinic to ensure compliance (administering Test Product to the infected diabetic foot ulcer and surrounding intact skin at a dose of 1 to 3 drops from a dropper bottle per 1 cm^2 of ulcer area, left open to air for 5 minutes and then dressed using Owens gauge, Kerlex and tape.). The patient will be scheduled for the next follow-up visit, with a reminder to bring the test article kit to the visit.

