### 14.2 Secondary Efficacy Endpoint Assessment

The primary efficacy endpoint is to assess the clinical response to bisphosphocinTM Nu-3 as determined by visual evaluation of the ulcer following Nu-3 treatment. The measurement of this variable will be determined by the DUSS score at screening, after a single dose treatment (Day 1), after a second dose treatment (Day 2), after twice daily for 7 day treatment, at Day 15.

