## 16.5 Analysis of Primary Outcome Measure

The microbiological response of Nu-3 to eliminate pathogenic bacteria will be determined for each group. Aerobic and anaerobic culture and sensitivity will be assessed at screening, after a single dose treatment (Day 1), after a second dose treatment (Day 2), after twice daily for 7 day treatment, at Day 15. An uncorrected chi-square analysis or a Fisher's Exact test will be used to compare each treatment group to the placebo group. An associated p-value less than 0.05 will be used to define statistical significance. An associated p-value less than 0.016 ( $0.05 \div 5$ ; Bonferroni correction) will be considered highly conclusive.

The clinical response of Nu-3 via visual evaluation of the ulcer will be determined for each group. DUSS Score will be assessed at screening, after a single dose treatment (Day 1), after a second dose treatment (Day 2), after twice daily for 7 day treatment, and at Day 15. An uncorrected chi-square analysis or a Fisher's Exact test will be used to compare each treatment group to the placebo group. An associated p-value less than 0.05 will be used to define statistical significance. An associated p-value less than 0.016 ( $0.05 \div 5$ ; Bonferroni correction) will be considered highly conclusive.

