## **8.2 Analysis of Efficacy Endpoints**

For each dose group, the proportion of subjects with a normal culture at the end of the MAD portion of the study will be compared to the proportion of subjects with a normal culture at the end of the MAD portion of the study for the combined placebo group using a Fisher's exact test. A subject with a normal culture at this time will be considered a success. Any subject with a missing value at the end of the MAD portion of the study will not be included in the analysis. A p-value less than 0.05 will be considered statistically significant and a p-value less than 0.0167, employing a Bonferroni correction for multiple comparisons, will be considered highly conclusive.

For continuous efficacy endpoints, data will be summarized descriptively at and a comparison using the Wilcoxon Rank Sum test between each of dose groups and the combined placebo group will be performed at each visit. For these endpoints, no imputation for missing values will be performed.

For categorical endpoints, a Fisher's exact test will be performed in a similar manner. Subjects missing a value for a secondary endpoint will be considered a failure (counted in the denominator) for that endpoint.

For all tests, a p-value less than 0.05 will be considered statistically significant and a p-value less than 0.0167, employing a Bonferroni correction for multiple comparisons, will be considered highly conclusive. Analysis for each secondary endpoint will be performed on the ITT population and the PP population.

Ulcer measurements and percentage of area reduction will be summarized descriptively by visit and statistical testing using a Wilcoxon Rank Sum test between each dose group and the combined placebo group. For all tests, a p-value less than 0.05 will be considered statistically significant. Analysis for each additional endpoint will be performed on the ITT population and the PP population.

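### The protocol labels the Day 1 culture and DUSS as post-dose, but its visit procedures collect them only before dosing; the Day 2 label is probably one dose ahead too

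*Protocol*

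**What the plan says.** **Timing labels.** Protocol 14.1 lists the culture assessments as screening, then "after a single dose treatment (Day 1), after a second dose treatment (Day 2"), then the end of the 7-day course and Day 15. Section 14.2 does the same for the "DUSS score at screening, after a single dose treatment (Day 1), after a second dose treatment (Day 2"). Section 16.5 repeats the list for both endpoints ("assessed at screening, after a single dose treatment (Day 1), after a second dose treatment (Day 2")) and follows it with chi-square or Fisher comparisons of each dose group with placebo, without saying which time points are tested.

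**Visit procedures.** Section 12.3 (Visit 2, Day 1) lists the visual examination, DUSS and swab ahead of the dosing paragraph, with the rider "Swab wound to culture for microbiological examination Not applicable if Visit 2 is the same day as Screening Visit". The synopsis has the same waiver. After dosing, the ulcer is dressed and the patient goes home with "verbal instructions to leave the bandage on the wound and return for a follow up visit" at about 24 hours. For Visit 3 (Day 2), section 12.4 opens with "Patients will return after the Single Ascending Dose Treatment" and lists "Baseline Patient Disease Assessment: Visual examination of chronic ulcer, score target ulcer using DUSS Scoring System, Swab wound to culture for microbiological examination". The investigator's check on continuation and the first observed dose of the twice-daily course come after that. The schedule of events shows one swab and one DUSS per visit.

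**SAP.** Section 8.1 summarises efficacy by visit and places statistical evaluation at the end of MAD. Section 8.2 tests normal culture at the end of MAD, but for continuous endpoints it says the Wilcoxon comparison "between each of dose groups and the combined placebo group will be performed at each visit". Baseline is defined only in section 9.2, for vital signs.

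**The concern.** The endpoint sections and the visit sections describe different samples under the same day numbers. Anyone who reports Day 1 by the labels in 14.1 or 16.5 would present a value from an untreated ulcer as the response to one dose. If Day 2 is also sampled before dosing, the only real single-dose reading in the trial would be credited to a second dose. Supporting the choice of dose range is a secondary objective (protocol 7.2), so the early response by dose group is something readers will look at.

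There is also an analysis consequence. The SAP uses change from baseline in DUSS and percentage reduction in ulcer area, but does not say which pre-dose value is the efficacy baseline. It also does not exclude the Day 1 visit from its by-visit tests.

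**Working it through.** The plan gives no figure to reproduce. The check sets the labels beside the procedures and then counts the tests affected.

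**1. Doses received when each sample is taken**

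| Time point | Label in 14.1, 14.2, 16.5 | Procedures (12.2 to 12.6, schedule) |
|---|---|---|
| Screening | before treatment | 0 doses |
| Day 1 | after dose 1 | 0 doses; no separate sample if same day as screening |
| Day 2 | after dose 2 | most likely 1 dose, about 24 h earlier |
| Day 9 | after the 7-day course | after the 7-day course |
| Day 15 | follow-up | follow-up |

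**2. Why Day 1 is settled.** Four features agree.
- The same-day waiver. Screening closes 4 hours before treatment, so a screening sample is always pre-dose. It can stand in for the Day 1 sample only if that sample is pre-dose too.
- The assessment is listed before the dosing paragraph.
- After dosing the ulcer is covered until the 24-hour visit, and no swab or DUSS is described in between.
- The schedule has a single entry per visit, with no split into pre-dose and post-dose.

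Where the protocol wants a Day 1 observation after dosing it says so, as it does for adverse events in 12.9 and 13.4. The three-cohort protocol in the same file (section 5.3) takes the Day 1 ulcer sample before treatment. That is corroboration only.

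**3. Why Day 2 is an inference.** Section 12.4 lists the swab and DUSS before the continuation check and the observed dose, and the schedule again has one sample. But only vital signs carry an explicit time before treatment. If the swab were taken after the observed dose, the Day 2 label would be right.

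**4. Day 1 tests under SAP 8.2.** DFI is not scored at Visits 2 and 3, so it drops out. The remaining continuous endpoints are DUSS change and eight ulcer measures (area, percentage area reduction, perimeter, maximum depth, mean depth, volume, length, width). The SAP has three dose groups, each compared with pooled placebo.
- If baseline is the screening value: (1 + 8) × 3 = 27 Day 1 comparisons. At the nominal 0.05 level, 27 × 0.05 = 1.35 chance findings expected.
- If baseline is the last pre-dose value, DUSS change and percentage area reduction are zero by construction wherever a Day 1 value exists. That leaves 7 × 3 = 21 comparisons, and 21 × 0.05 = 1.05 expected.

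These are counts for one analysis population; the SAP runs ITT and PP. They read the by-visit rule for continuous endpoints as covering the ulcer measures. The SAP's separate paragraph on those measures summarises them by visit but does not repeat the visit rule for the test.

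**The case against.** The strongest reply is that the protocol defers analysis detail to the SAP, and the SAP never uses the single-dose or second-dose labels. It tabulates by visit, and its culture test, on the endpoint of section 14.1, is made only at the end of MAD. A Day 1 row in a by-visit table is a pre-dose group comparison and misleads only if someone calls it a response. This stands, and it limits the point. A reader might infer that the trial's efficacy result will rest on pre-treatment values; the documents do not support that.

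Three other stronger readings also fail.
- That Day 2 is proven to be mislabelled. The heading word baseline proves little, since the protocol also calls the Day 9 and Day 15 laboratory tests baseline. The Day 2 case rests on listing order and the single sample.
- That screening, up to 7 days earlier, has been made the efficacy baseline. No section says so; the efficacy baseline is simply undefined. For DUSS the choice should seldom matter, because pulses, probing to bone, ulcer location and ulcer number are unlikely to change within a week.
- That on a same-day Visit 2 the screening value becomes the Day 1 value. The procedure is waived and no carry-over is stated, so there is no separate Day 1 value.

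The reply does not remove the contradiction. Section 16.5 attaches placebo comparisons to the mislabelled list, and SAP 8.2 tests at each visit without excluding the pre-dose one, in tension with SAP 8.1.

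**Conclusion.** The concern holds in a limited form. The Day 1 label is wrong: the procedures yield no efficacy value after the first dose on Day 1. The Day 2 label is probably wrong by one dose, on the assumption that the listing order in 12.4 is the order in which things are done. So one of five labelled time points is shown to be misdescribed, and a second is likely to be.

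The effect is confined to the single-dose and second-dose readings under 16.5 and to the Day 1 Wilcoxon tests of DUSS change and ulcer measurements, in which the true drug effect is zero (21 to 27 tests per population, about 1.05 to 1.35 chance findings at the nominal level). The end-of-MAD culture test, the DFI analyses, the safety conclusions and dose escalation are untouched. Efficacy is secondary in a pilot with no sample-size calculation. The correction should be made before analysis, but the point does not undermine the trial's main purpose.

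**What to change.** - **Protocol 14.1, 14.2 and 16.5:** reconcile with 12.3 and 12.4. Label Day 1 as pre-dose baseline and Day 2 as 24 hours after the single dose. In 12.4, confirm and state that the swab and DUSS precede the Day 2 dose.
- **SAP 8.1 and 8.2:** apply the section 9.2 baseline definition (last available value before study drug) to the efficacy endpoints, which also covers patients screened and dosed on the same day. Exclude Day 1 from the post-baseline between-group tests, and settle whether testing is at each later visit or only at the end of MAD.
- **If post-dose samples were intended:** 12.3, 12.4 and the schedule do not collect them on Day 1 or specify them on Day 2, and would have to be reconciled with the endpoint sections instead.

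The relabelling costs wording in the three endpoint sections, a clarifying sentence in 12.4 and short additions to SAP section 8. It needs no extra visits, samples or patients.
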